3.2. Rationale

TDF was approved for the treatment of CHB in the U.S. in 2008 and in China in 2013. TDF is recommended as the first line anti-viral therapy either for naïve patients or as a rescue regimen by CHB clinical practice guidelines based on its high potency in supressing HBV DNA, good tolerance profile and low incidence of drug resistance [Chinese Medical Association, 2015, Sarin, 2016, Terrault, 2016, EASL, 2017]. Two global registered multicentred, randomized, controlled Phase III studies, GS-US-174-0102 (NCT00117676; Study 102) and GS-US-174-0103 (NCT00116805; Study 103), have shown that, during 48 weeks of TDF treatment period, 76.0% hepatitis B envelope antigen (HBeAg) positive and 93% HBeAg negative CHB patients achieved complete viral suppression (defined as HBV-DNA<69IU/ml, 400copies/ml) [Marcellin, 2008]; 98.0% and 99.6% achieved complete viral suppression among HBeAg positive and HBeAg negative respectively during 8 years of treatment [Marcellin, 2014]. No cases of TDF drug resistance were observed through the 8 years of treatment [Corsa, 2015]. The 48-week Chinese multicentred, randomized, controlled Phase III trials showed similar reports and the following open-label study up to 192 weeks reported similar results [Hou, 2015, Hou, 2016].

Besides the high potency of TDF in viral suppression, TDF was well-tolerated in the 8-years follow-up studies 102 & 103 [GS-US-174-0102 and GS-US-174-0103) and 192-week follow-up Phase III study from China [Hou, 2016]. For Studies 102 & 103, no renal toxic effects were observed during the 48 weeks of TDF treatment among patients with CHB who had preserved renal function at baseline; and the incidence of all individual renal adverse events in the 8-year follow up period was reported $\leq 2.2\%$ (either ≥ 0.5 mg/dL increase in serum creatinine, or serum phosphate ≤ 2 mg/dL, or creatinine clearance ≤ 50 mL/min). Nearly 1% of renal adverse events was observed in the long-term follow up period in the Chinese Phase III study [Hou, 2016]. In TDF global registry study, BMD was also monitored, it was observed that T scores of hip and spine were stable between years 4-8.

Since launch, accumulating data from observational or real-world studies have added to our understanding of the efficacy and safety of TDF: the VIREAL study conducted in France, the GEMINIS in Germany, and a Taiwanese study [Marcellin, 2016, Petersen, 2015, Wang, 2016]. In these studies, treatment-naïve and experienced patients from diverse practice settings who were newly initiated on TDF therapy, were included. Hypertension, diabetes, renal disease, cardiovascular diseases, and other comorbidities were present in approximately 40% of patients, with up to 28% having estimated glomerular filtration rate (eGFR) <90 ml/min. The primary measurement of treatment effectiveness was HBV DNA suppression. HBV DNA suppression was achieved by >89% of those completing 3 years of treatment with no incidences of drug resistance. However, there have been inconsistent conclusions associated with the safety. In GEMINIS cohorts, the mean eGFR decreased by -3.50 mL/min over 3 years of TDF treatment. Similar findings were reported in the Taiwanese study where the greatest decrease in eGFR occurring in the first year (from 96.0 ± 32.4 to 88.3 ± 21.1). While the

VIREAL study showed that median eGFR was not remarkably affected during the 3-years of treatment even in patients aged ≥65 years old or patients having baseline creatinine clearance of <90ml/min. In the 3-year retrospective analyses done by Wang et al [Wang, 2016]. Mean eGRF reduced in the first year of TDF treatment. However, it did not decrease significantly during 2-3 years of treatment; but BMD did not change significantly during the treatment.

The effectiveness and renal safety results of TDF varies between registered clinical trials [complete virological response (CVR) over 95%] and real-world research (CVR approximately 71 to 92%) [Pol, 2012, Idilman, 2015, Kim, 2015], partly due to the difference between clinical trial patient population and real world study population. Phase III clinical trials are conducted under well-controlled conditions among pre-selected patients with strict in/exclusion criteria, generally eliminating older patients and those with co-infections or comorbidities (such as cirrhosis). Compared with most patients seen in real world practice, those participating in clinical trials are typically younger and healthier with less comorbidity and better treatment adherence. Understanding how antivirals perform in real world general patient population is more important to guide routine clinical practice. The results from high-quality real-world cohorts will continue to provide clinical guidance for physicians by providing safety and effectiveness evidence across diverse treatment settings and in a broader array of patients and enable more patients to benefit from the available treatment options.

Lampertico et al. [Lampertico, 2016] reviewed recent real-world evidence on the safety of TDF treatment among HBV-monoinfected patients. Overall, TDF can lead to minor reduction in eGFR and BMD, which was mainly observed during early stage of treatment and remained stable in long-term follow up in most patients. Although TDF was well tolerated with no clinically significant renal toxicity, evidence from cohort studies seems to be conflicting. Reductions in GFR/Creatinine among HBV patients treated with TDF were reported, the clinical significance of these changes needs more discussion and the degree of association between TDF and changes in renal function indicators varies across studies. The inconsistency might result from small sample size, different baseline population with different renal function, varying measures of renal function. Few studies observed BMD during TDF treatment among CHB patients. Gill et al. carried out a single-centre cohort study in the UK, specifically to assess the impact of TDF on BMD in 170 HBV-monoinfected patients. There was no difference in T-score between treatment groups for lumbar or femoral neck measures, but TDF was associated with a lower hip T-score compared with no TDF (P = 0.02) [Gill, 2015].

Since launching in China since 2014, the treatment experience of TDF is limited due to its late entry, high price, and lack of real world evidence on long-term effectiveness and safety of TDF among Chinese CHB patients to guide clinical practice. Safety outcomes among CHB patients in existing real-world studies were inconsistent due to limited sample size, different patient's socio-demographic and clinical characteristics, and varying clinical criteria for renal function assessment. In addition, there is a general concern on renal safety of TDF among Chinese HCPs because of the NUC-associated renal toxicity observed in HIV-infected patients, although it was assumed to be mostly related to either co-medication or co-morbidities associated with HIV.

Therefore, the primary purpose of the current real-world study is to evaluate the long-term effectiveness of TDF in the treatment of Chinese CHB patients. A secondary purpose is to explore TDF safety among Chinese CHB patients to address HCPs' concerns. The real-world data collected from this study will provide clinical guidance to Chinese HCPs, and aid public health decision making on resource allocation.

3.3. Benefit/Risk Assessment

Not applicable for this non-interventional real-world study.

4. OBJECTIVES AND RESEARCH QUESTIONS

Study objectives and research questions are listed in the Table 2.

Table 2 Objectives and Research Questions

Objectives	Research Questions
Primary Objective To assess the effectiveness among overall and sub-group Chinese CHB patients who receive TDF treatment in real-world	Among the overall analysis population and relevant sub-group* populations: • Proportion of patients who achieve complete virologic response (CVR) at
	 weeks of 48, 96, and 144. Proportion of patients who achieve HBeAg loss and/or HBeAg. seroconversion in HBeAg positive patients at weeks of 48, 96 and 144.
	 Proportion of patients who achieve HBsAg loss and/or HBsAg seroconversion at weeks of 48, 96 and 144.
	 Proportion of patients who achieve transaminase normalization at weeks of 48, 96 and 144.
	 Time to CVR, defined as time from baseline to the first occurrence of CVR (if applicable)
Secondary Objective	
To assess the renal function change among overall and sub-group CHB patients during TDF	Among the overall analysis population and relevant sub-group* populations:
treatment	 Proportion of patients whose eGFR decline >20% from baseline at weeks of 48, 96,

Objectives	Research Questions
	and 144.
	 Percentage of change from baseline in eGFR at weeks of 48, 96, and 144
	Change from baseline in eGFR values at weeks of 48, 98 and 144
	 Proportion of patients with confirmed serum phosphate Grade 3 or 4 abnormality (<2.0 mg/dL) at weeks of 48, 98 and 144.
	 The percentage of change from baseline in serum phosphate at weeks of 48, 98 and 144.
	 Change from baseline in phosphorus values at weeks of 48, 98 and 144
Exploratory Objectives	
To explore the Bone Mineral Density (BMD) change among overall and sub-group CHB patients during TDF treatment	Percentage of BMD change from baseline at weeks of 48, 96, and 144
To investigate predictors of effectiveness among CHB patients who receive long-term	Baseline or on-treatment predictors (e.g. baseline characteristics, etc).
TDF treatment	Treatment effectiveness, including CVR, HBeAg loss and/or HBeAg, transaminage normalization
To explore risk factors of safety among CHB patients who receive long-term TDF treatment	Baseline or on-treatment risk factors (e.g. baseline characteristics, co-morbidities, and concomitant treatment etc).
	Renal impairment, including eGFR decline and serum phosphate
	Bone impairment, including BMD decline
To investigate patient adherence to therapy	Duration of TDF therapy during the study period

Objectives	Research Questions
	Summary of reasons of treatment discontinuation
To summarize the spontaneous AEs/SAEs and pregnancy exposures occurred during the study period (with special interest in AEs/SAEs due to TDF)	Summary of the occurrence of spontaneous AEs/ SAEs and pregnancy cases by GSK products and categorization.
	Incidence of decompensated cirrhosis/liver disease and related complications, at weeks of 48, 98 and 144

Abbreviations:

AEs = Adverse events; CHB = Chronic hepatitis B; CVR = Complete virological response; DNA = Deoxyribonucleic acid; eGFR = estimated Glomerular filtration rate; HBV = Hepatitis B virus; HBeAg = Hepatitis B envelope antigen; HCC = Hepatocellular carcinoma; MDRD = Modification of Diet in Renal Disease; SAEs = Serious adverse events * Sub-group of interest may include important baseline socio-demographic, health behaviour, and clinical characteristics.

According the relevance and importance to the clinical practice and patient outcomes, sub-groups are defined by patients sociodemographic, health behaviour and clinical characteristics and on treatment factors, including age, gender, baseline HBV DNA level, HBeAg status, baseline alanine aminotransferase level in relation to the upper limit of the normal range, receipt or no-receipt of previous treatment with other NUCs, previous history of drug resistance, comorbidities (e.g. chronic kidney disease, hypertension, diabetes), baseline renal function, patient treatment adherence, etc.

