9.3. Statistical Analyses

A detailed Reporting and Analysis Plan (RAP) outlining details of data analyses will be created and described below. Besides the 144-week analysis, key analyses may be conducted annually with the 48-week and 96-week cut-off data to look at short-term patient outcomes. No adjustment for multiplicity will be made for these analyses.

Continuous variables will be summarized for overall population and various subgroups using mean (standard deviation) and/or median (range), while categorical variables will be summarized in tables of frequencies and percentages. Comparative analyses will be performed across sub-groups using Student's t test or analyses of variance for quantitative variables, and Pearson's Chi-square test (Fisher exact test might be used when necessary) for qualitative variables. Nonparametric tests will be used when necessary.

In primary and secondary analyses, as this is a real-world study without mandatory scheduled visits, the assessments (e.g. lab test) may not be conducted exactly at 6-month intervals, but to keep the robustness of the estimation for effectiveness and renal function change, a time window that ± 28 days for week 48, 96 and 144 will be applied in each cut-off analyses. As the supportive analyses, the analyses with time windows that ± 3 months will be conducted. More details will be included in Reporting and Analyses Plan (RAP).

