9.3.3. Secondary Analyses

Patients' renal functional change during TDF treatment period will be explored.

- The proportion of patients whose eGFR (MDRD equation) decline >20% from baseline at weeks of 48, 96 and up to week 144 will be summarized for the overall study analysis population and sub-group populations.
- Mean and 95% confidence intervals for the change from baseline in eGFR values will be calculated for the overall analysis population, as well as for the subpopulations of interests. A mixed effect model will be fitted to explore the impacts on the mean change from baseline in eGFR of fixed effects of age, gender, treatment-naïve or experienced, ADV or non-ADV, type of baseline comorbidities (Cirrhosis, Hypertension, diabetes mellitus (DM), non-overlapping), baseline eGFR values, baseline HBV-DNA counts, baseline HBeAg status, and other factors as appropriate, and random effects of subject ID.
- The percentage of change from baseline in eGFR will be estimated for the overall analysis population and by sub-populations at weeks 48, 96, and 144. Figures of mean eGFR values overall and the sub-populations of interests will be generated.
- The proportion of patients with confirmed a serum phosphate Grade 3 or 4 abnormality (<2.0 mg/dL) at weeks of 48, 98 and 144 will be summarized for the overall study analysis population and sub-group populations.
- The percentage of change from baseline in serum phosphate will be estimated for the overall analysis population and by sub-populations at weeks 48, 96, and 144. Figures of mean serum phosphate values overall and the sub-populations of interests will be generated.
- Mean and 95% confidence intervals for the change from baseline in serum phosphate values will be calculated for the overall analysis population, as well as for the sub-populations of interests. A mixed effect model will be fitted to explore the impacts on the mean change from baseline in serum phosphate of fixed effects of age, gender, treatment-naïve or experienced, ADV or non-ADV, type of baseline co-morbidities (Cirrhosis, Hypertension, DM, non-overlapping), baseline eGFR values, baseline HBV-DNA counts, baseline HBeAg status, baseline phosphorus and other factors as appropriate, and random effects of subject ID.

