12. STUDY LIMITATIONS

This is a China-based multi-centre, prospective, longitudinal, non-interventional study conducted in a real-world setting in order to investigate long-term effectiveness and safety of TDF among Chinese CHB patients to guide clinical practice. The absence of comparison group is one of the major limitations to this study, which can be mitigated by a historical comparison leveraging previous trial data from literature or in-house alternatively. The mixing of the new initiator and on-treatment patients is another limitation, which may complicate the analysis due to varied treatment duration and inconsistent baseline information. Potential solutions include setting restriction on the inclusion criteria to the patients who have already started TDF prior to the entry of study in line with those of new initiators.

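### Comparing eGFR change across baseline eGFR, with the same single value used as classifier and subtracted, makes low-baseline patients appear to lose less and high-baseline patients more than they do

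*Protocol*

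**What the plan says.** Section 4 ends its list of subgroup factors with "baseline renal function, patient treatment adherence, etc". Its secondary objective asks for eGFR change and percentage change overall and by subgroup.

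Section 9.3.3 carries this out: "Mean and 95% confidence intervals for the change from baseline in eGFR values will be calculated for the overall analysis population", and likewise for the subpopulations of interest. It adds a regression: "A mixed effect model will be fitted to explore the impacts on the mean change from baseline in eGFR" of a list of fixed effects that includes "baseline eGFR values, baseline HBV-DNA counts, baseline HBeAg status", with a random effect for subject. The serum phosphate model has the same form, with baseline phosphorus as a fixed effect.

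Section 9.3 sets the general rule for contrasts: "Comparative analyses will be performed across sub-groups using Student's t test or analyses of variance for quantitative variables". Section 12 concedes that "The absence of comparison group is one of the major limitations to this study". Nowhere does the protocol describe a replicate or averaged baseline, or any allowance for regression to the mean.

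**The concern.** A single eGFR value is the patient's underlying level plus laboratory error and short-term fluctuation. Call that error e. Patients classed as low have, on average, a negative e, and patients classed as high a positive one. The outcome subtracts the same value, so -e enters every change score. Low-baseline patients drift upward and high-baseline patients downward even if TDF affects all of them alike.

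The mixed model does not remove this. All change scores of one patient share the same baseline error, and the covariate contains it too. A random subject intercept leaves that correlation in place. With no control arm, nothing cancels it, and the historical comparison suggested in Section 12 does not act within baseline strata.

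Section 3.2 says the safety part of the study is meant to address prescribers' concern about renal effects, and it cites stability in patients with low baseline clearance in another cohort. The contrast between impaired and normal baseline function is therefore one that readers will look for, and it is the one that this artefact distorts.

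**Working it through.** **No eGFR figure to reproduce.** The protocol states precision only for complete virologic response. That figure checks: 2000 × 0.65 = 1300 completers, and 1.96 × √(0.8 × 0.2 / 1300) = 0.0217, against the stated 0.022. The 1300 is used below.

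**Inputs from Section 3.2.** The Taiwanese cohort's eGFR moved "from 96.0 ± 32.4 to 88.3 ± 21.1" in the first year. The German cohort's mean three-year change was -3.50 mL/min.

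**Assumptions, not in the documents.** A true loss of 3.5 in every patient; baseline mean 96 with SD 32.4 (20 as an alternative); equal SDs at both times; cut-offs at 60 and 90; reliability ρ of a single baseline value of 0.95, 0.90 or 0.80. Under a uniform true change, ρ is also the correlation of baseline with follow-up.

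**Formula.** Expected observed change in a group = -3.5 + (1 - ρ) × (96 - group's mean baseline).

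With SD 32.4, the normal distribution gives a mean baseline of 43.7 below 60 and 118.2 at or above 90. The distances from 96 are 52.3 and -22.2. At ρ = 0.90 the below-60 group shows -3.5 + 0.10 × 52.3 = +1.7, and the other group -3.5 - 0.10 × 22.2 = -5.7.

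| Group, SD | ρ 0.95 | ρ 0.90 | ρ 0.80 |
|---|---|---|---|
| <60, SD 32.4 | -0.9 | +1.7 | +7.0 |
| ≥90, SD 32.4 | -4.6 | -5.7 | -7.9 |
| <60, SD 20 | -1.3 | +0.9 | +5.3 |
| ≥90, SD 20 | -4.1 | -4.7 | -6.0 |

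Every cell should read -3.5.

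**Where the apparent loss vanishes.** Set (1 - ρ) × distance = 3.5. For <60: 3.5 / 52.3 = 0.067, so ρ is about 0.93 (SD 32.4); 3.5 / 43.9 = 0.080, so about 0.92 (SD 20). For <90, with distances 29.8 and 20.0: about 0.88 and 0.82.

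**Baseline coefficient.** With no true dependence, the slope of change on baseline is -(1 - ρ): -0.05, -0.10, -0.20. In a simple regression at one visit with n = 1300, t ≈ -(1 - ρ) / √((1 - ρ²) / 1300), which gives -5.8, -8.3 and -12.0.

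**Decline above 20%.** A simulation under the same assumptions (SD 32.4, baselines of 10 or less dropped) gives these proportions for <60 against ≥90: 21.7% and 3.6% at ρ 0.95; 22.6% and 10.5% at 0.90; 21.0% and 21.0% at 0.80; 18.5% and 28.1% at 0.70. This outcome does not follow the pattern of the mean.

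**What the Taiwanese SDs can show.** Projecting follow-up as 88.3 + ρ(21.1 / 32.4)(baseline - 96.0), a patient at 66 changes by +2.8 at ρ = 1.0 and +6.7 at 0.8, and one at 126 by -18.2 and -22.1. But at ρ = 1.0 there is no random error, so that part comes wholly from the fall in SD. With equal SDs and the same mean change of -7.7, regression to the mean alone gives -7.7 + (1 - ρ) × 30 at 66: -4.7 at ρ 0.9 and -1.7 at 0.8. Both are losses.

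**The case against.** **The criticised test is partly inferred.** The t test/ANOVA sentence is generic and allows nonparametric alternatives. Section 4's footnote says only that subgroups may include such characteristics. The subgroup list in Section 9.3.2 omits baseline renal function and names renal disease, a recorded condition rather than a split on the subtracted value. This softens the point but does not remove it: Section 4 names the factor, Section 9.3.3 reports change for subpopulations, and the model names baseline eGFR outright.

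**Adjusting change for baseline is standard.** This stands for the other factors in the model. It does not cover the baseline coefficient itself, which the text lists among the impacts to be explored.

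**The study is descriptive, and details may sit in the analysis plan.** That plan could add a remedy. But the protocol already fixes the outcome, the covariate and the aim, so a plan that follows it inherits the fault.

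**Creatinine is measured in a central laboratory from study entry.** This narrows analytical error but not biological fluctuation.

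**Stronger readings that the documents do not support.** A reader might infer that impaired patients are bound to look stable or improved. That needs reliability at or below about 0.92 to 0.93 for <60, or 0.82 to 0.88 for <90, and the protocol gives no within-patient variability. A reader might also take the Taiwanese SDs as measuring the artefact. They are compatible with it but cannot separate it from true differential decline, outliers or a changed set of patients.

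**Conclusion.** The point holds for the mean (and, in direction, the percentage) change in eGFR contrasted across baseline renal function, and for the baseline eGFR coefficient in the change model. The direction follows from the design: apparent loss is too small in low-baseline groups and too large in high-baseline groups. The size rests on assumed reliability, cut-offs, SD and a uniform true loss. In the illustration, the spurious gap between <60 and ≥90 runs from 3.7 mL/min (-0.9 against -4.6, ρ 0.95) to 14.9 (+7.0 against -7.9, ρ 0.80) at SD 32.4. Even at high reliability the low group wrongly appears to lose less.

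The point does not extend to the overall mean change, since no eligibility criterion selects on eGFR, or to baseline eGFR used to adjust for other factors. Nor does it support a blanket claim of bias towards reassurance in the proportion with more than 20% decline. It is a correction worth making before analysis; it does not threaten the primary objective.

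**What to change.** In Section 9.3.3, for the question of baseline renal function:

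- Model the eGFR values at all visits with baseline as one of the outcomes and subject random effects for level and change. Enter time as visit categories or in pieces (early and later periods). A single straight slope would misfit the early fall followed by stability described in Section 3.2. Report change against the model-based starting level.
- Keep tables of change by baseline-eGFR group as descriptive only, without t test or ANOVA. Comparison with published strata remains possible.
- State that the baseline eGFR coefficient in the change model serves for adjustment and is not read as a risk factor.
- Apply the same rules to baseline phosphorus in the serum phosphate model.

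The cost is a somewhat more complex analysis and report, and the separation of error from early change then rests on the model's variance assumptions. No new data are needed.
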